Cytokine distribution and vital signs over time are analysed by a repeated measures ANOVA (mixed models), if significant followed by the Bonferroni post-hoc test.

Data is tested for normality using Kolmogorov-Smirnov-test

HISTORY OF CHANGES

Changes from version 3.1 of the study protocol, dated 08 January 2018

- Introduction of retrospective data collection and exploratory post-hoc analysis of
 - Additional SOFA score data to replace data treated as missing in the original analysis
 - Duration of ICU stay
- Implementation of non-substantial change on plasma sample use documented on note to file dated 08 October 2018

Study protocol version 4.0 applies to study sites outside of France only

Changes from version 2.1 of the study protocol, dated 31 October 2017

- Addition of an interim analysis (section 15.4)
- Clarification of concomitant medication recording
- Minor corrections and clarifications

Study protocol version 3.0 dated 04 January 2017 applies to study sites outside of France only

Changes from version 1.3 of the study protocol, dated 12 September 2017

- Addition of blood samples for DNA analyses related to the TREM-1 signalling pathway
- Addition of a paragraph detailing the analysis and storage of blood samples
- Blood levels of sTLT-1 will not be analysed
- Name change of IMP management provider implemented
- Rating of Adverse Events updated for consistency with eCRF
- Minor corrections and clarifications

Study protocol version 2.0 dated 31 October 2017 applies to study sites outside of France only

Changes from version 1.2 of the study protocol, dated 29 August 2017

- Minor corrections and clarifications on the timing of blood samples in tables 1 and 2

These changes are **classified as non-substantial** by the sponsor according to the EU Clinical Trials Directive and section 8.2 of this study protocol.

Study protocol version 1.2, dated 29 August 2017 implemented the following changes from version 1.0 of the study protocol, dated 20 February 2017

- Changes requested by the French ANSM for sites in France:
 - Addition of exclusion criterion “APACHE II score <14”
 - Measurements of interferon- γ on days 1, 3, 5 and 28
 - Additional timepoint for the measurement of anti-drug antibodies on day 10
 - Direct antibody test (direct Coombs) at baseline (pre-dose), days 10 and 28
 - Addition of free bilirubin to the biochemistry laboratory parameters
 - Update of SUSAR reporting requirements for France
- Minor corrections and clarifications

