7 STUDY OBJECTIVES

Primary

- To evaluate the safety and tolerability of MOTREM in patients with septic shock

Secondary

- To evaluate the effects of MOTREM exposure over up to 5 days in patients with septic shock
- To evaluate the PK/PD and dose/PD relationships to TREM-1 pathway related markers
- To evaluate the effect of MOTREM on transcriptomics
- To evaluate the effect of MOTREM on clinical parameters (e.g. vasopressor doses, vasopressor-free days, ventilator-free days, mortality)

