9 SELECTION OF PATIENTS

9.1 Number and Source of Patients

A total of 48 patients is planned. There will be 12 patients in stage 1 (4 per dose level) and 36 patients in stage 2 (9 per dose level). No formal sample size calculation was performed. The number of patients was chosen on the basis of similar studies investigating the safety, tolerability and pharmacokinetics of a drug product. In stage 1, the patients will be treated in three sequential cohorts with ascending dose levels of 4 patients each. Stage 2 of the study has a parallel-group design, where three dose levels of MOTREM will be compared to placebo.

Patients admitted to the participating intensive care units (ICUs) for septic shock will be screened at admission for eligibility. The eligibility criteria are identical between the two stages of the study.

The maximum number of patients according to the adaptive features of the study protocol will not exceed 66 patients, as specified below:

- Each cohort in stage 1 can be repeated once for the collection of additional safety data
- In each cohort in stage 1, one patient not completing 24 hours of study drug infusion will be replaced

At sites, who are conducting more than one clinical trial competing for the same patient population, a selection bias should be avoided. Random allocation of patients with the diagnosis to the different trials is an acceptable method for the minimisation of such bias and is recommended (19). A respective procedure should be in place at these sites.

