15.1 Statistical Methods

15.1.1 General Considerations

The analysis will be computed with SAS Version 9.4 (Copyright© 2013 by SAS Institute Inc., Cary, NC, USA).

Unless otherwise specified, baseline is defined as the last planned assessment prior to first dosing and no subgroup analysis is currently planned.

Missing safety, pharmacodynamic, pharmacokinetic and clinical data will not be replaced and will be treated as missing from summary and statistical analyses.

Unless otherwise specified, all treatment comparisons will be two-sided and significance will be assessed at the 5% level.

All safety, pharmacokinetic, pharmacodynamic and clinical data will be summarised by treatment group (Placebo, Dose level 1, Dose level 2 and Dose level 3), and visit, as appropriate.

Qualitative variables will be presented using the number of patients, the number of missing values, the frequency and the percentage per modality.

Quantitative variables will be reported using the number of patients, the number of missing values, the mean, the standard deviation, the median, the first and the third quartiles, the minimum and the maximum.

Between groups comparisons are calculated using an independent t-test or ANOVA-test for quantitative variables with a parametric distribution, or Mann-Whitney test or Kruskal Wallis-test for variables with a non-parametric distribution.

Data is tested for normality using Kolmogorov-Smirnov-test.

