15.1.5 Safety Analyses

Adverse events will be coded using the MedDRA dictionary version 18.1 or higher. Treatment emergent adverse events (events start after the first dose of investigational treatment or events present prior the administration of investigational treatment and worsened during the study (increased in severity)) will be classified by primary system organ class, preferred term and treatment group. Separate summaries will be performed for study medication related events, death, serious adverse events, adverse events leading to discontinuation of study medication and other adverse events of interest.

Other safety parameters that will be assessed include safety laboratory parameters (haematology, coagulation, biochemistry, arterial blood gases etc), vital signs (SBP, DBP, heart rate and body temperature), ECG and exposure of MOTREM. The parameters will be listed by treatment group (Placebo, Dose level 1, Dose level 2 and Dose level 3), patient and visit and summarised using standard descriptive statistics. All abnormal values will be identified in patient data listings. Changes from baseline will be described.

PD Analyses: Pharmacodynamic data will be listed by treatment, patient, and visit/time. Summary statistics will be provided by treatment and visit/time. Geometric means and CV will be presented for the primary and secondary PD endpoints.

PD endpoints will be compared between treatments with an ANOVA on logs. Each MOTREM dose group will be compared to placebo with a contract t-test at the 2-sided 10% level.

PK Analyses: Observed MOTREM serum concentrations will be summarised by treatment and corresponding time when sampling occurred. Derived PK parameters will be summarised by treatment.

Clinical Analyses: Several clinical parameters as the clinical events related to sepsis and its complications, the SOFA score total and each sub-score (respiratory, cardiovascular, hepatic, coagulation, renal and neurological system), the vasopressor use, the mechanical ventilation and intubation will be described by treatment group and visit. Standard descriptive statistics will be used.

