15.2 Determination of Sample Size

A formal sample size calculation was not performed for the primary objective of the study. Instead, the sample size 48 patients overall (N=12 for each dose level) was chosen to provide sufficient data for this pilot study of MOTREM in patients with septic shock. This is in line with recommendations for sample size of pilot studies (23).

As this is an exploratory study no adjustments for multiplicity will be employed.

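### The dose/PD and PK/PD objective has no stated analysis that uses dose order or LR12 concentration

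*Combined protocol and SAP*

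**What the plan says.** Section 7 and the synopsis list as a secondary objective "To evaluate the PK/PD and dose/PD relationships to TREM-1 pathway related markers".

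The PD paragraph sits within section 15.1.5. It states that "PD endpoints will be compared between treatments with an ANOVA on logs", and then that "Each MOTREM dose group will be compared to placebo with a contract t-test at the 2-sided 10% level". That level departs openly from the default in section 15.1.1: "Unless otherwise specified, all treatment comparisons will be two-sided and significance will be assessed at the 5% level". The PK paragraph provides only for summaries of concentrations and derived parameters by treatment. Section 15.1.3 names biomarker profiles and AUCs as secondary PD variables and labels PD exploratory.

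On multiplicity, section 15.2 says "As this is an exploratory study no adjustments for multiplicity will be employed". The synopsis has a different rule for some of the same markers: "Cytokine distribution and vital signs over time are analysed by a repeated measures ANOVA (mixed models), if significant followed by the Bonferroni post-hoc test".

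Sections 15 and 15.1.3 defer further detail to a separate SAP.

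**The concern.** The objective asks about a relationship: does the marker response change with dose, and with measured LR12? An ANOVA across four unordered groups gives the same result if the dose labels are shuffled. Each dose-versus-placebo contrast uses two group means and ignores where that dose lies on the scale. Neither yields a slope, and no stated analysis brings a concentration and a PD value together for the same patient.

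Sections 6.3 and 8.5.1 say the data are meant to help design later studies, and dose is central to that use. Without an ordered analysis and an exposure analysis fixed in advance, the dose question would be answered by looking across three separate comparisons, for several markers and visits.

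**Working it through.** **1. The plan's sample size.** Section 9.1: "There will be 12 patients in stage 1 (4 per dose level) and 36 patients in stage 2 (9 per dose level"). Section 15.2: "the sample size 48 patients overall (N=12 for each dose level"). Check: 3 cohorts × 4 = 12 and 4 groups × 9 = 36, total 48. Each active dose has 3 + 9 = 12 patients and placebo has 3 × 1 + 9 = 12 (section 15.3). The stated 48, at 12 per group, reproduces if the stages are pooled.

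**2. What each stated analysis uses.**

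| Stated analysis | Uses dose order? | Uses LR12 concentration? |
|---|---|---|
| ANOVA on logs (15.1.5) | no | no |
| Each dose vs placebo, 10% (15.1.5) | no | no |
| Repeated-measures ANOVA, cytokines (synopsis) | no | no |
| PD summaries by treatment and time (15.1.5) | only by eye | no |
| PK summaries by treatment (15.1.5) | only by eye | not linked to PD |

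**3. Power of the candidate tests.** The documents give no effect size or SD, so the shapes below are assumptions, in SD units on the log scale. With n = 12 per group, df = 48 − 4 = 44 and the two-sided 10% critical t is 1.680. For weights w and means μ, the noncentrality is Σwμ / √(Σw²/12). The log doses are ln 0.3 = −1.20, ln 1 = 0 and ln 3 = 1.10. They are almost equally spaced, so the active-dose slope is close to high minus low.

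| Test (weights: placebo, low, middle, high) | Even rise 0, ⅓, ⅔, 1 | Flat 0, 1, 1, 1 | Peaked 0, 0.5, 1, 0.5 |
|---|---|---|---|
| Trend (−3, −1, 1, 3), SE √(20/12) = 1.291 | 3.333/1.291 = 2.58: 82% | 3/1.291 = 2.32: 74% | 2/1.291 = 1.55: 45% |
| Active slope (0, −1, 0, 1), SE √(2/12) = 0.408 | 0.667/0.408 = 1.63: 49% | 0: 10% | 0: 10% |
| High vs placebo, SE 0.408 | 2.45: 78% | 2.45: 78% | 1.22: 33% |
| Middle vs placebo | 1.63: 49% | 2.45: 78% | 2.45: 78% |
| Low vs placebo | 0.82: 21% | 2.45: 78% | 1.22: 33% |
| Any of the three pairwise (simulated) | 83% | 94% | 82% |

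Using stage 2 alone (9 per group, df 32), the even rise gives 71% for the trend and 40% for the active slope.

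**4. False positives under no effect, per marker and time point.** For three 10% contrasts sharing one placebo group (correlation 0.5, df 44), the chance of at least one is 23.4% by numerical integration and 23.3% by simulation of 400,000 trials. Assuming independence would give 1 − 0.9³ = 27.1%. If the contrasts were read only after a significant overall F test, the rate would be 8.8% (F at 10%) or 4.7% (F at 5%), but section 15.1.5 states no such gate.

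**The case against.** Four points on the other side have force.

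- **The pairwise contrasts are not the only PD test.** There is also the overall ANOVA and, for cytokines, the repeated-measures route in the synopsis. Dose ordering can be read from the summaries, and the objective says evaluate, not test. This stands, but none of these gives an ordered or exposure-based estimate.
- **A reader might infer that the 23% is an error in the plan.** It is not. Section 15.2 discloses the absence of adjustment and gives the reason, and a loose level is a defensible screening choice in a 48-patient pilot. The figure is a caution for reading isolated hits. It would not apply to cytokines handled by the Bonferroni route.
- **A reader might infer that one trend contrast should replace the pairwise ones.** The table does not support that. The gain over the top-dose contrast is small (82% against 78%) and reverses for the flat shape (74% against 78%). For the peaked shape the middle-dose contrast does much better than the trend (78% against 45%). A trend that includes placebo also rejects 74% of the time when all doses act alike. That shape is not far-fetched, since every active arm gets the same loading dose (section 8.5.3).
- **The separate SAP may already close the gap.** That cannot be checked from the supplied text.

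**Conclusion.** The mismatch holds for the supplied text: a secondary objective on dose/PD and PK/PD relationships, with no stated analysis that uses dose order or concentration. It is worth correcting, but its weight is limited, because PD is exploratory and safety is the primary endpoint.

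The benefit of the correction is a direct answer to the stated question, not a large gain in power. Only the active-dose slope separates a dose relationship from a uniform drug effect (10% rejection under the flat shape, against 74% for the trend), and its power is modest: about 49% for an even rise to 1 SD. The 90% interval for high minus low would be about ±1.680 × 0.408 = ±0.69 SD. Both ordered analyses are therefore mainly for estimation.

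The figures assume pooled stages, 12 evaluable patients per group, a common SD on the log scale and reviewer-chosen effect shapes. The familywise rate barely depends on pooling (23.3% at 9 per group).

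Separately, the Bonferroni step in the synopsis conflicts with the unadjusted contrasts in 15.1.5 and the no-adjustment statement in 15.2.

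**What to change.** Keep the ANOVA on logs and the three dose-versus-placebo contrasts, reported as estimates with intervals. Add to the SAP, within the same model:

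1. One ordered trend contrast over placebo and dose levels 1 to 3, described as a test of an ordered drug effect.
2. The slope on log dose among the three active groups, with its interval, described as the dose-relationship estimate.
3. A regression of log PD response on measured LR12 concentration in MOTREM-treated patients, for the PK/PD part.

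Name a lead marker. sTREM-1 is the natural one, because Table 2 samples it and PK daily on days 1 to 5. Use time-matched samples drawn during infusion, or a fixed early window, and not an AUC of varying length. Infusion length depends on vasopressor withdrawal, early stoppers have the end-of-infusion assessments once only (section 11.3.3), and missing data are not replaced (section 15.1.1). With a half-life of about 2 minutes (section 9.6), a sample 10 minutes after the infusion stops is 5 half-lives on, at about (½)⁵ = 3% of the earlier level.

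Reconcile the synopsis rule for cytokines with 15.1.5 and 15.2, and state that isolated positive contrasts will be read in light of the 23% per-marker figure.

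The cost is two contrast statements, one regression and the definition of a window and a concentration measure; no new samples are needed. Section 15.4 has the SAP final before unblinding. Section 15.5 already refers to an original analysis, so if unblinding has taken place these additions must be labelled post hoc.

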13 ADVERSE EVENTS

13.1 Adverse Events

Safety will be determined by an evaluation of physical examination, vital signs, ECG parameters, laboratory tests and by the occurrence of Adverse Events (AEs).

Adverse event (AE): Any untoward medical occurrence in a patient or clinical study subject administered a medicinal product and which does not necessarily have a causal relationship with this treatment. Events occurring prior to the first administration are part of baseline information.

An adverse event (AE) can therefore be any unfavourable and unintended sign (including an abnormal laboratory finding), symptom, or disease temporally associated with the use of an investigational medicinal product, whether or not considered related to the investigational medicinal product.

Adverse reaction (AR): All untoward and unintended responses to an IMP related to any dose administered.

All adverse events judged by either the reporting investigator or sponsor as having a reasonable suspected causal relationship to an investigational medicinal product are qualified as adverse reactions. The expression reasonable causal relationship means that there is evidence or argument to suggest a causal relationship.

Multiple signs or symptoms: If an AE consists of several signs or symptoms that can be represented by one single syndrome or diagnosis, the syndrome or diagnosis will be recorded in the CRF as the AE instead of the individual signs or symptoms.

Worsening: Signs, symptoms, syndromes or diagnoses present before the first administration of the IMP will be considered as AEs if they worsen after the start of the IMP.

AE collection: The condition of the patients will be monitored throughout the study from the time of signed Informed Consent up to the end of the study (day 28). The investigator will collect the AEs reported spontaneously, observed, or elicited in response to a non-leading question (for example, "How have you been feeling since we last asked you?"). The investigator will record all AEs in the source records and the eCRF.

Study specific definition:

Clinical events related to severe sepsis or sepsis complications are recorded on the appropriate eCRFs (see section 12.9). When serious, these clinical events are exempt from serious adverse event reporting, unless the investigator deems the event to be related to the administration of the study drug. The following events will be considered clinical events related to severe sepsis or sepsis complications:

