- Death related to severe sepsis, that is, related to severe sepsis or a sequela of sepsis based on the interpretation of the investigator.
- Cardiovascular events: the need for vasoactive drugs, hypotension.
- Respiratory events: decreased $\text{PaO}_2/\text{FiO}_2$, mechanical ventilation, hypoxia, acute respiratory distress syndrome, acute lung injury, or respiratory failure.
- Hepatic events: hepatic injury or liver dysfunction that leads to an increase from baseline in the serum level of bilirubin or other LFTs.
- Renal events: renal failure, renal insufficiency, or renal injury that leads to an increase from baseline in serum creatinine.
- Hematologic/coagulation events: coagulopathy, disseminated intravascular coagulation, thrombocytopenia, or thrombocytosis.
- Systemic inflammatory response syndrome related criteria: tachypnea, hypopnea, leukocytosis, leukopenia, hypothermia, hyperthermia, tachycardia, or bradycardia.

AE rating:

The assessment of intensity of an AE will be made using the following general categorical descriptors:

Mild	No interference with the patient's daily activities and does not require mandatory corrective/symptomatic treatment
-------------	---

Moderate Moderate interference with the patient's daily activities and/or requires minimal medical intervention or corrective treatment required

Severe Major and unacceptable interference with the patient's daily activities and requires mandatory corrective/symptomatic treatment, possible hospitalisation

The investigator should use clinical judgment in assessing the intensity of events not directly experienced by the patient (e.g., laboratory abnormalities).

The causal relationship of AEs will be rated as either **related** or **unrelated** to the IMP.

The causal relationship of a SAE to the IMP will be rated as follows:

Unrelated Clearly and incontrovertibly due only to extraneous causes, and does not meet criteria listed under unlikely, possible or probable.

Unlikely Does not follow a reasonable temporal sequence from administration of the IMP, or is most likely related to another etiology than the trial drug such as the patient's clinical state, environmental factors or other therapies.

Possible Follows a reasonable temporal sequence from administration of the IMP, and/or a causal relationship cannot be excluded and remains likely.

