15.1.3 Endpoints

Safety and tolerability will be the primary endpoint and it will be monitored during the course of the study as specified below:

Safety and Tolerability Parameters

- Vital signs: systolic (SBP) and diastolic (DBP) blood pressure, heart rate, and body temperature.
- ECG (12-lead ECG)
- Safety laboratory tests: haematology, coagulation, plasma biochemistry.
- Presence of anti-LR12 antibodies
- Adverse events: from screening until study completion.

Secondary endpoints include the following:

Pharmacokinetics

Plasma concentrations of LR12 will be measured by a validated LC-MS/MS assay and analysed using non-compartmental methods to obtain estimates of the PK parameters.

Pharmacodynamics (exploratory)

The concentration profiles of biomarkers (sTREM-1, immune and vascular related biomarkers) over time and biomarker mRNA levels will be analysed.

Clinical Parameters

- Resolution of organ dysfunction (SOFA score total and individual domains)
- Vasopressor use
- Invasive mechanical ventilation
- Renal support
- Time until shock reversal defined as cessation of vasopressor support for 24 hours
- Mortality at day 28 and day 90

Safety and tolerability will be the primary endpoint and in addition, the exposure of MOTREM will be analysed. The biomarker concentration profiles over time and the area under the concentration (AUC) curves will be analysed as secondary PD variables.

The MOTREM concentration profile over time and the main derived PK parameters will be analysed as PK endpoints.

The endpoints and their analysis will be further specified in the statistical analysis plan (SAP).

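### The protocol does not settle whether sepsis-type organ events are also adverse events, and no table described in 15.1.5 counts patients across both streams, so the AE and SAE tables may under-show organ events

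*Combined protocol and SAP*

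**What the plan says.** Section 15.1.3 sets the aim: "Safety and tolerability will be the primary endpoint". Its components are vital signs, ECG, safety laboratory tests, anti-LR12 antibodies and adverse events.

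Section 13.1 carries a study-specific definition inside the adverse event section: "Clinical events related to severe sepsis or sepsis complications are recorded on the appropriate eCRFs (see section 12.9". It continues: "When serious, these clinical events are exempt from serious adverse event reporting, unless the investigator deems the event to be related" to the study drug. The list is wide. Examples are "Cardiovascular events: the need for vasoactive drugs, hypotension"; "Hepatic events: hepatic injury or liver dysfunction that leads to an increase from baseline in the serum level of bilirubin or other LFTs"; and "Renal events: renal failure, renal insufficiency, or renal injury that leads to an increase from baseline in serum creatinine". It also covers hypoxia and respiratory failure, thrombocytopenia and coagulopathy, leukopenia, tachycardia, bradycardia and sepsis-related death.

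Section 13.3 says that every serious or non-serious AE goes in the relevant eCRF section. It also makes laboratory, vital-sign and ECG findings AEs when the investigator judges them clinically relevant deteriorations from screening. It does not mention the section 12.9 events.

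Section 15.1.5 has two separate streams. Treatment-emergent AEs are MedDRA coded and "will be classified by primary system organ class, preferred term and treatment group", with further summaries for deaths, SAEs, related events and discontinuations. "Several clinical parameters as the clinical events related to sepsis and its complications" come in a later paragraph, Clinical Analyses, and are described by treatment group and visit with standard descriptive statistics.

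**The concern.** Several entries on the 13.1 list name an organ finding and give no criterion for telling a sepsis effect from a drug effect. A rise in creatinine or bilirubin, a fall in platelets or a new bradycardia can be read as a sepsis event, as an AE, or as both. Where the event is serious, the only written override is the investigator's opinion that the drug caused it. With a drug not previously given to patients with septic shock (section 8.5.1), that opinion is weak evidence; the comparison of randomised arms is meant to replace it.

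If sites resolve the label differently, the same kind of event is counted in the AE table for one patient and on the clinical-event pages for another. A dose-related excess could then be divided between two summaries with different units: patients by preferred term in one, descriptions by visit in the other. With 12 patients per arm there is little room for such dilution.

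**Working it through.** **1. Is the routing settled?** Set the sections side by side.

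| Section | What it settles | What it leaves open |
|---|---|---|
| 12.9 / 13.1 | Sepsis-type events have their own eCRF pages | Whether they are also entered as AEs |
| 13.1 | Serious ones are exempt from SAE reporting unless judged related | Any exemption from AE recording |
| 13.3 | All AEs go on the AE section; relevant laboratory, vital-sign and ECG deteriorations are AEs | Whether section 12.9 events are included or must be entered twice |
| 15.1.5, AE paragraph | MedDRA coding, a treatment-emergent rule, tables by system organ class and preferred term | Whether section 12.9 events are in these tables |
| 15.1.5, Clinical Analyses | Section 12.9 events by group and visit | Coding, an onset rule, a count of patients with at least one event |

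Two sites could follow this text in good faith and enter the same event differently. The lists in 12.9 and 13.1 also differ by one term: hyperthermia appears only in 13.1.

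**2. Arm size.** Stage 1 gives 3 patients per dose and stage 2 gives 9, so 3 + 9 = 12 per dose. Placebo is 3 × 1 + 9 = 12. The total is 4 × 12 = 48, which matches sections 9.1 and 15.2.

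**3. Illustration of dilution.** The documents give neither an organ-event rate nor the share of such events entered as AEs, so both are assumptions. Let p be the true proportion of patients in an arm with a given organ event, and f the share entered as AEs. With one event per patient and independent labelling, the number X seen in the AE table is binomial (12, pf), and

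P(X ≥ 3) = 1 − Σ (k = 0 to 2) C(12, k) (pf)^k (1 − pf)^(12 − k).

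For p = 0.25:

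- f = 1, pf = 0.25: 1 − (0.0317 + 0.1267 + 0.2323) = 0.609
- f = 0.75, pf = 0.1875: 1 − (0.0828 + 0.2292 + 0.2909) = 0.397
- f = 0.5, pf = 0.125: 1 − (0.2014 + 0.3453 + 0.2713) = 0.182
- f = 0.25, pf = 0.0625: 1 − (0.4610 + 0.3688 + 0.1352) = 0.035

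That is 61%, 40%, 18% and 4%. Over a range of rates:

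| p | f = 1 | f = 0.75 | f = 0.5 | f = 0.25 |
|---|---|---|---|---|
| 0.10 | 11% | 6% | 2% | 0.3% |
| 0.20 | 44% | 26% | 11% | 2% |
| 0.30 | 75% | 53% | 26% | 6% |
| 0.50 | 98% | 89% | 61% | 18% |

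The direction is the same at every rate. The size depends almost wholly on f, which the plan leaves undefined.

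**The case against.** The strongest reply is that nothing is excluded. The only express exemption concerns SAE reporting, and it lapses when the investigator judges the event related. Section 13.1 asks for all AEs to be recorded and treats worsening of pre-existing conditions as an AE; 13.3 has no carve-out; 13.2.1 requires fatal AEs to be reported whatever their cause. This stands. A reader might infer that sepsis-type events are kept out of the treatment-emergent tables, but the documents do not say so. What they support is that the matter is unsettled.

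Second, the primary safety endpoint is wider than AEs. Section 15.1.5 also summarises haematology, coagulation, biochemistry, blood gases, blood pressure, heart rate, temperature and ECG by arm, with changes from baseline and abnormal values identified in listings. SOFA sub-scores are described by arm as well. This also stands: a reader might infer that the safety analysis would miss organ toxicity altogether, and that goes too far. The signal would be split, not lost. The backstop is still partial. Summaries by visit do not count patients with an event, and section 15.1.1 leaves missing values unreplaced, so patients who die contribute nothing to later visits.

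Third, section 15 defers detail to a separate SAP whose text is not in the document reviewed. It may settle the point, so the absence of coding, an onset rule or a combined table can be asserted only of 15.1.5 as written.

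Fourth, expected disease events are handled apart on purpose, and pooling them raises the background in every arm. That is fair, and it is why the combined table should sit beside the existing tables and not replace them.

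**Conclusion.** The point holds as an unresolved ambiguity with a consequence for the AE and SAE tables, and it should be fixed. The protocol does not determine whether a hypotensive, respiratory, hepatic, renal, platelet/coagulation or heart-rate event labelled as sepsis also enters the AE form. No table described in 15.1.5 makes the result independent of that label.

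The percentages above are illustration only. They rest on assumed event rates, assumed shares, independent labelling and a threshold of 3 patients chosen for display. They describe the AE table alone, not the whole safety analysis. It would be tempting to restate them as lost statistical power, but the plan describes AEs by arm and specifies no between-group test for them, so there is no planned power to lose.

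**What to change.** 1. Reconcile sections 12.9, 13.1 and 13.3: state whether each listed event is also an AE and, if so, whether it is entered on both pages. Align the two lists.
2. State in 15.1.5 or the SAP whether the treatment-emergent AE and SAE tables include these events.
3. Add one table by treatment group of all AEs plus all section 12.9 events that start or worsen after the first dose, regardless of attributed cause. Code them in MedDRA, present them by system organ class and preferred term, count each patient once per term, and remove events entered on both pages. Keep the existing AE and clinical-event tables beside it.

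The cost is MedDRA coding of the section 12.9 events, a rule for matching double entries, one table and a few sentences of text. The documents do not say whether the clinical-event pages record onset dates; if they do not, the rule on onset after first dose would need dates from source data. The drawback is a higher background rate in every arm of the combined table, which the placebo column lets the reader judge.
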